8.6 ET subgroup analysis

As defined in section 3.1, The ET population is a subset of the Safety population and as such will be grouped based on the study drug they took, rather than the group to which they were randomised. The data of the ET population will be analysed in order to determine the reasons for the withdrawal and will explore the last available ALT, HbA1c, and other assessment variables. The timing of the withdrawal will also be assessed in addition to a summary of baseline values for any similarities the population may share.

8.7 Other safety analyses

Physical examination results will be summarised using descriptive statistics with change from Baseline and tabulated by visit. At Screening, a full physical examination will be performed, but from Baseline through the follow-up period, a targeted physical examination will be performed.

9. INTERIM ANALYSES

An interim analysis is planned when 80 subjects have completed the full 24 week study period. The analysis population will include data from those 80 subjects up to and including week 24, in addition to all early terminations (up to and including week 24) and all remaining currently randomised subjects with post-baseline data prior to the 28th of February 2017. Populations in the interim analysis will use the same definitions as the full analysis at the end of the study.

The purpose of this interim analysis will be to establish the safety of the study treatment, identify signals of efficacy of the two dose groups (600mg and 1200mg) against Placebo and to set sample size parameters for potential future studies. As a result, the critical probability for the interim analysis will be 0.00305, which requires the final alpha level to be 0.04695. All populations will be analysed for the interim analysis as described above.

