## 12.4 Statistical Analysis Plan

A detailed SAP in which all aspects of data analysis will be defined in detail and prepared prior to the blind break.

The SAP will include details of the following:

- Definitions of analysis populations
- Description of any data transformations and data derivations to be used together with rationale and references
- Details of the statistical methods to be conducted, together with methods used to estimate corresponding confidence intervals
- Details of methods for checking the appropriateness of the chosen statistical model
- Discussion of the use of covariates and subgroups
- Discussion of any multiplicity and adjustment procedures to be implemented.
- Methods of dealing with missing values and outliers together with details of any sensitivity analyses to be performed
- Specification of any subgroup or interaction analyses
- Example table and listing shells to indicate the proposed presentation of the data.

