2.2 Study design

This was to be a randomized, double blind, placebo controlled, 3-arm parallel group, multi-dose, multi-centre study. The three treatment arms include 600mg IMM-124E three times daily, 1200mg IMM-124E three times daily and matching placebo. A total of 120 subjects, randomised to the three treatment groups in 1:1:1 ratio, having been previously diagnosed with NASH will be studied during a 24 week treatment period.

An interim analysis will be planned for this study, the purpose of which will be to determine whether any safety concerns exist as well as identify any preliminary signals for efficacy through examination of the primary, secondary and exploratory endpoints. The interim analysis will occur when 80 subjects have completed the 24 weeks treatment period and have both Baseline and 24 weeks' evaluable MRI hepatic fat fraction values. Each IMM-124E dose group will be compared to the placebo treatment group using pairwise contrasts. This analysis will occur for each of the hepatic fat fraction strata because of a differential response pattern across strata that have been noticed in previous studies on NASH (Le et al., 2012; Loomba et al., 2015).

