3. ANALYSIS POPULATIONS AND GENERAL STATISTICAL METHODOLOGY

This analysis plan is based on version 1.3 of the protocol, dated 8 May 2016, and includes other changes discussed at a later date.

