3.3 General statistical methodology

Treatment groups will be described as '600 mg IMM-124E', '1200 mg IMM-124E' and 'Placebo'. All tables, figures and listings will be produced for these three treatment groups. In addition, where specified, tables will be produced where subjects are grouped by baseline hepatic fat fraction, baseline HbA1c, and with a binary classification (not treated vs. treated).

General descriptive statistics for continuous measures will include number of observations (n), mean, standard deviation (SD), median, quartiles, minimum and maximum. For categorical variables, descriptive statistics will include n and percentage occurrence within the treatment group. The denominator for calculating percentage will be the number of valid observations within the treatment group.

For the basic and interim analysis, missing data will remain missing and not be imputed. However, for sensitivity measures in the final study analysis, missing values will also be imputed using a multiple imputation technique (Berglund, 2010 and Yuan, 2011).

This is a multicentre study, but no analysis using centre as a stratification factor will be performed, except for the primary endpoint, in which case the analysis will be performed on the imputed data both with and without centre as a stratification factor as a sensitivity analysis on the primary endpoint. Analysis of centre as a stratification factor will also be performed on ALT, AST, Glucose, A_{1c}, lipid profile parameters and CK-18.

Concomitant medications will be coded using the most recently available version of the World Health Organisation Drug Dictionary (WHO DD) at the time of data lock. Medications will be summarised and tabulated using the first and second levels of the dictionary. Medical history and adverse events will be coded using the most recently available version of the Medical Dictionary for Regulatory Affairs (MedDRA) at the time of data lock. Both medical history and adverse events will be summarised and tabulated using System Organ Class and Preferred Terms.

Patients given the wrong treatment will be analysed as randomised for efficacy measures (for the ITT, PP and FAS populations) and as treated for safety measures (Safety population and ET subgroup).

For safety data, if there are unscheduled visits where data values exist and those data are missing for the prior, scheduled, visit, then the values from the unscheduled visit will be imputed.

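### SAP 9: an interim level of 0.00305 does not require a final level of 0.04695, and no passage says the SAP's interim rule replaces the protocol's

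*SAP*

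**What the plan says.** **SAP.** Section 9 sets the timing: "An interim analysis is planned when 80 subjects have completed the full 24 week study period". Section 2.2 gives the same count, requires those subjects to have "evaluable MRI hepatic fat fraction values" at Baseline and Week 24, and gives the total: "A total of 120 subjects, randomised to the three treatment groups in 1:1:1 ratio". On the levels, section 9 says "the critical probability for the interim analysis will be 0.00305, which requires the final alpha level to be 0.04695". It gives no boundary, spending function or information fraction. The levels are introduced as following from the purposes of the interim, one of which is "to set sample size parameters for potential future studies"; none of those purposes implies a significance level.

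**Protocol.** Section 12.8 places the look at 22 or more subjects with verified MRI. It sets 0.0000147 for the interim and 0.0499 for the final analysis, and derives them from a two-sided O'Brien-Fleming spending function at 25% information. The synopsis places the look at 30 or more subjects.

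**Which text governs.** Protocol 12.4 lists among the contents of the SAP "Discussion of any multiplicity and adjustment procedures to be implemented". SAP 3 says the SAP is based on protocol version 1.3 and "includes other changes discussed at a later date". SAP 10 lists no changes and leaves their documentation to the final study report.

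**The concern.** There are two problems.

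- **The derivation is stated wrongly.** The SAP presents 0.04695 as a necessary consequence of 0.00305. Subtraction treats the two looks as if their rejection probabilities simply added. The final data contain the interim data, so the two test statistics are correlated and the subtraction gives up some alpha.
- **The current texts carry three triggers (22, 30 and 80) and two final levels (0.0499 and 0.04695).** No sentence says which interim rule applies. A final p-value between 0.04695 and 0.0499 changes verdict with the document used. A reader who combined the SAP's interim level with the protocol's final level would slightly exceed 0.05.

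The threshold for the final analysis should be identifiable before the blind is broken, not reconstructed in the study report.

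**Working it through.** **Inputs**
- Overall two-sided alpha 0.05 for one active-versus-placebo comparison (protocol 12.1).
- SAP levels 0.00305 and 0.04695, look at 80 (SAP 9); total 120 (SAP 2.2). Information fraction t = 80/120 = 0.667.
- Protocol levels 0.0000147 and 0.0499, basis 25%, trigger at least 22 (protocol 12.8); synopsis trigger at least 30.
- 40 per arm, difference of 5 points, SD of 6 at each time point, correlation 0.25 (protocol 12.1).

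**1. The SAP's figure.** 0.05 − 0.00305 = 0.04695 exactly, which is a Bonferroni split.

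**2. Overall error of that pair.** With interim and final statistics Z1 and Z2 bivariate normal, correlation √t, and critical values c1 and c2:

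overall error = 1 − P(|Z1| < c1, |Z2| < c2).

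At t = 0.667, 0.00305 gives c1 = 2.963 and 0.04695 gives c2 = 1.987. The result is **0.0474**.

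**3. Final level that uses the full 0.05.** Keep 0.00305 at the interim and solve the same equation for c2 with overall error 0.05:

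| Information fraction | Final level using the full 0.05 | Overall error of 0.00305/0.04695 |
|---|---|---|
| 0.50 | 0.0490 | 0.0480 |
| 0.60 | 0.0494 | 0.0476 |
| 0.667 (80/120) | **0.0496** | **0.0474** |
| 0.70 | 0.0497 | 0.0473 |
| 0.75 | 0.0498 | 0.0471 |

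Fractions other than 0.667 are assumed, to show sensitivity. None of them gives 0.04695.

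**4. Where 0.00305 may come from.** The only method named in either document is O'Brien-Fleming spending. In its two-sided form the alpha spent is 4[1 − Φ(2.2414/√t)], where 2.2414 is the 0.9875 normal quantile.

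| Look | t | Alpha spent |
|---|---|---|
| 22/120 | 0.183 | 0.00000033 |
| 30/120 | 0.25 | 0.0000147 |
| 60/120 | 0.50 | 0.00305 |
| 80/120 | 0.667 | 0.0121 |

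The function reproduces the protocol's interim level at 25%, which is the synopsis's 30 subjects; 22 of 120 is 18.3%. It returns 0.00305 at 50% information. At the SAP's own 80/120 it would spend 0.0121 and leave a final level of 0.0463. That the SAP took 0.00305 from a 50% look is an inference; the SAP does not say so.

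**5. Mixed pair.** 0.00305 with the protocol's final 0.0499 gives an overall error of 0.0503 at t = 0.667.

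**6. Practical size.** The SD of change is 6 × √(2 × (1 − 0.25)) = 7.348. The standard error of a difference is 7.348 × √(2/40) = 1.643. With 78 degrees of freedom and the noncentral t distribution:

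| Final level | Smallest significant difference | Power for 5 points |
|---|---|---|
| 0.04695 | 2.0187 × 1.643 = 3.32 | 0.846 |
| 0.0496 | 1.9944 × 1.643 = 3.28 | 0.851 |
| 0.0499 | 1.9917 × 1.643 = 3.27 | 0.852 |

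**The case against.** The strongest reply is that nothing is numerically wrong. Under an additive split 0.00305 does leave 0.04695, and the pair keeps the error below 0.05 at any information fraction. That robustness has value here. The interim data also include early terminations and other randomised subjects, enrolment is at least 120, and protocol 11.5 replaces withdrawals, so the fraction is not fixed in advance. The SAP is also the natural governing text, given protocol 12.4 and SAP 3. The mixed pair is hypothetical, and the protocol's trigger of 22 is a minimum that a look at 30 satisfies. The trial is exploratory, makes no adjustment for two doses or several endpoints, and by protocol 12.8 does not stop for success or failure.

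Most of this stands. The pair does not inflate the error, a split is a legitimate choice, and the effect is small. Two things remain. The SAP does not describe its pair as a split; it says one level forces the other, which is untrue. The passages that favour the SAP are general, do not mention the interim, and are accompanied by a section that defers all changes to the study report. The exploratory label waives adjustment for endpoints and treatment comparisons, but both documents chose to adjust for the interim look, so that adjustment should be stated correctly.

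**Conclusion.** The concern holds, at minor severity. An interim level of 0.00305 does not require 0.04695. The SAP pair is a conservative Bonferroni split with overall error 0.0474 at 80/120, where 0.0496 would use the full 0.05. The cost is about 0.006 in power and 0.04 fat points in the smallest significant difference. The larger practical defect is that two final levels and three triggers stand in current text with no statement that one set replaces the others.

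These figures assume an information fraction of 80/120, a single dose-versus-placebo comparison, normal test statistics for the error rates, and the protocol's own variance assumptions. The actual fraction may differ, but the final level that uses the full 0.05 stays between 0.0494 and 0.0497 for fractions from 60% to 70%.

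**What to change.** Before any unblinding, amend SAP 9 and SAP 10 to:

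1. State that the 80-subject trigger and one pair of levels supersede protocol 12.8 and the synopsis.
2. Remove the claim that the interim level requires the final one, and name the method.
3. Keep 0.00305 at the interim and compute the final level from the actual information fraction (0.0496 at 80/120).
4. Define that fraction as subjects with an evaluable post-baseline MRI in the interim primary analysis, divided by the actual number in the final primary analysis, with replacements for withdrawals counted in the denominator. SAP 3.3 makes MRI availability the right count: "For the basic and interim analysis, missing data will remain missing and not be imputed".

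If the interim has already been unblinded, do not relax the final level: keep 0.00305/0.04695 and label it a Bonferroni split.

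The cost is two or three sentences in the SAP, with no change to data collection or sample size. Editing protocol 12.8 and the synopsis as well would be a protocol modification, which section 13.1.4 sends to the ethics committee and the regulator.

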10. CHANGES FROM THE PROTOCOL

Any changes from version 1.3 of the protocol dated 8 May 2016 will be documented in the final study report.

12. TABLE AND FIGURE LISTINGS

Table Section	Table Title (Population)
Section 10.1	Subject disposition (usually from Clean File document)
Section 10.2	Protocol deviations (usually compiled by medical writers from listing)
Section 11.1	Analysis populations
Section 11.2	Demographics (FAS population)
	Prior Medical History events (FAS population)
	Current Medical History events (FAS population)
	Prior medications ceased before study treatment (FAS population)
	Concomitant medications taken during study (FAS population)
	New medications commenced after start of study treatment (FAS population)
	Histological results from liver biopsy prior to Screening (FAS population)
Section 11.3	Compliance (ITT, PP, FAS populations)
Section 11.4	Hepatic fat fraction (ITT population)
	Analysis of change in hepatic fat fraction (ITT population)
	Hepatic fat fraction (FAS population)
	Analysis of change in hepatic fat fraction (FAS population)
	Hepatic fat fraction (PP population)
	Analysis of change in hepatic fat fraction (PP population)
	Analysis of hepatic fat fraction using multiple imputation and analysis method (ITT population)
	Analysis of hepatic fat fraction using multiple imputation and analysis method (FAS population)
	Analysis of hepatic fat fraction with site as stratification factor (ITT population)
	Analysis of hepatic fat fraction with site as stratification factor (FAS population)
	Analysis of hepatic fat fraction with site as stratification factor (PP population)
	Hepatic fat fraction with Hepatic fat fraction sub-groups as stratification factor (ITT population)
	Hepatic fat fraction with Hepatic fat fraction sub-groups as stratification factor (FAS population)
	Hepatic fat fraction with Hepatic fat fraction sub-groups as stratification factor (PP population)
	Hepatic fat fraction with Fibrosis sub-groups as stratification factor (ITT population)
	Hepatic fat fraction with Fibrosis sub-groups as stratification factor (FAS population)
	Hepatic fat fraction with Fibrosis sub-groups as stratification factor (PP population)
	Hepatic fat fraction with Ballooning sub-groups as stratification factor (ITT population)
	Hepatic fat fraction with Ballooning sub-groups as stratification factor (FAS population)

population)

Hepatic fat fraction with Ballooning sub-groups as stratification factor (PP population)

Hepatic fat fraction with HbA1c sub-groups as stratification factor (ITT population)

Hepatic fat fraction with HbA1c sub-groups as stratification factor (FAS population)

Hepatic fat fraction with HbA1c sub-groups as stratification factor (PP population)

Hepatic fat fraction with Inflammation sub-groups as stratification factor (ITT population)

Hepatic fat fraction with Inflammation sub-groups as stratification factor (FAS population)

Hepatic fat fraction with Inflammation sub-groups as stratification factor (PP population)

Hepatic fat fraction with ALT sub-groups as stratification factor (ITT population)

Hepatic fat fraction with ALT sub-groups as stratification factor (FAS population)

Hepatic fat fraction with ALT sub-groups as stratification factor (PP population)

Hepatic fat fraction with outliers excluded (ITT population)

Hepatic fat fraction with outliers excluded (FAS population)

Hepatic fat fraction with outliers excluded (PP population)

ALT area under the curve values for 24 weeks of treatment (ITT population)

ALT area under the curve values for 24 weeks of treatment (FAS population)

ALT area under the curve values for 24 weeks of treatment (PP population)

ALT area under the curve values for 24 weeks of treatment with hepatic fat fraction sub-groups as stratification factor (ITT population)

ALT area under the curve values for 24 weeks of treatment with hepatic fat fraction sub-groups as stratification factor (FAS population)

ALT area under the curve values for 24 weeks of treatment with hepatic fat fraction sub-groups as stratification factor (PP population)

ALT area under the curve values for 24 weeks of treatment with HbA1c sub-groups as stratification factor (ITT population)

ALT area under the curve values for 24 weeks of treatment with HbA1c sub-groups as stratification factor (FAS population)

ALT area under the curve values for 24 weeks of treatment with HbA1c sub-groups as stratification factor (PP population)

ALT area under the curve values for 24 weeks of treatment with Fibrosis sub-groups as stratification factor (ITT population)

ALT area under the curve values for 24 weeks of treatment with Fibrosis sub-groups as stratification factor (FAS population)

ALT area under the curve values for 24 weeks of treatment with Fibrosis sub-groups as stratification factor (PP population)

ALT area under the curve values for 24 weeks of treatment with Ballooning sub-groups as stratification factor (ITT population)

ALT area under the curve values for 24 weeks of treatment with Ballooning sub-groups as stratification factor (FAS population)

ALT area under the curve values for 24 weeks of treatment with Ballooning sub-groups as stratification factor (PP population)

ALT area under the curve values for 24 weeks of treatment with Inflammation sub-groups as stratification factor (ITT population)

ALT area under the curve values for 24 weeks of treatment with Inflammation sub-groups as stratification factor (FAS population)

ALT area under the curve values for 24 weeks of treatment with Inflammation sub-groups as stratification factor (PP population)

ALT area under the curve values for 24 weeks of treatment with ALT sub-groups as stratification factor (ITT population)

ALT area under the curve values for 24 weeks of treatment with ALT sub-groups as stratification factor (FAS population)

ALT area under the curve values for 24 weeks of treatment with ALT sub-groups as stratification factor (PP population)

AST area under the curve values for 24 weeks of treatment (ITT population)

AST area under the curve values for 24 weeks of treatment (FAS population)

AST area under the curve values for 24 weeks of treatment (PP population)

AST area under the curve values for 24 weeks of treatment with hepatic fat fraction sub-groups as stratification factor (ITT population)

AST area under the curve values for 24 weeks of treatment with hepatic fat fraction sub-groups as stratification factor (FAS population)

AST area under the curve values for 24 weeks of treatment with hepatic fat fraction sub-groups as stratification factor (PP population)

AST area under the curve values for 24 weeks of treatment with HbA1c sub-groups as stratification factor (ITT population)

AST area under the curve values for 24 weeks of treatment with HbA1c sub-groups as stratification factor (FAS population)

AST area under the curve values for 24 weeks of treatment with HbA1c sub-groups as stratification factor (PP population)

AST area under the curve values for 24 weeks of treatment with Fibrosis sub-groups as stratification factor (ITT population)

AST area under the curve values for 24 weeks of treatment with Fibrosis sub-groups as stratification factor (FAS population)

AST area under the curve values for 24 weeks of treatment with Fibrosis sub-groups as stratification factor (PP population)

AST area under the curve values for 24 weeks of treatment with Ballooning sub-groups as stratification factor (ITT population)

AST area under the curve values for 24 weeks of treatment with Ballooning sub-groups as stratification factor (FAS population)

AST area under the curve values for 24 weeks of treatment with Ballooning sub-groups as stratification factor (PP population)

AST area under the curve values for 24 weeks of treatment with Inflammation sub-groups as stratification factor (ITT population)

AST area under the curve values for 24 weeks of treatment with Inflammation sub-groups as stratification factor (FAS population)

AST area under the curve values for 24 weeks of treatment with Inflammation sub-groups as stratification factor (PP population)

AST area under the curve values for 24 weeks of treatment with ALT sub-groups as stratification factor (ITT population)

AST area under the curve values for 24 weeks of treatment with ALT sub-groups as stratification factor (FAS population)

AST area under the curve values for 24 weeks of treatment with ALT sub-groups as stratification factor (PP population)

GGT area under the curve values for 24 weeks of treatment (ITT population)

GGT area under the curve values for 24 weeks of treatment (FAS population)

GGT area under the curve values for 24 weeks of treatment (PP population)

GGT area under the curve values for 24 weeks of treatment with hepatic fat fraction sub-groups as stratification factor (ITT population)

GGT area under the curve values for 24 weeks of treatment with hepatic fat fraction sub-groups as stratification factor (FAS population)

GGT area under the curve values for 24 weeks of treatment with hepatic fat fraction sub-groups as stratification factor (PP population)

GGT area under the curve values for 24 weeks of treatment with HbA1c sub-groups as stratification factor (ITT population)

GGT area under the curve values for 24 weeks of treatment with HbA1c sub-groups as stratification factor (FAS population)

GGT area under the curve values for 24 weeks of treatment with HbA1c sub-groups as stratification factor (PP population)

GGT area under the curve values for 24 weeks of treatment with Fibrosis sub-groups as stratification factor (ITT population)

GGT area under the curve values for 24 weeks of treatment with Fibrosis sub-groups as stratification factor (FAS population)

GGT area under the curve values for 24 weeks of treatment with Fibrosis sub-groups as stratification factor (PP population)

GGT area under the curve values for 24 weeks of treatment with Ballooning sub-groups as stratification factor (ITT population)

GGT area under the curve values for 24 weeks of treatment with Ballooning sub-groups as stratification factor (FAS population)

GGT area under the curve values for 24 weeks of treatment with Ballooning sub-groups as stratification factor (PP population)

GGT area under the curve values for 24 weeks of treatment with Inflammation sub-groups as stratification factor (ITT population)

GGT area under the curve values for 24 weeks of treatment with Inflammation sub-groups as stratification factor (FAS population)

GGT area under the curve values for 24 weeks of treatment with Inflammation sub-groups as stratification factor (PP population)

GGT area under the curve values for 24 weeks of treatment with ALT sub-groups as stratification factor (ITT population)

GGT area under the curve values for 24 weeks of treatment with ALT sub-groups as stratification factor (FAS population)

GGT area under the curve values for 24 weeks of treatment with ALT sub-groups as stratification factor (PP population)

Proportion of subjects with normal ALT by visit (FAS population)

Proportion of subjects with normal ALT by visit (ITT population)

Proportion of subjects with normal ALT by visit (PP population)

Proportion of subjects with normal ALT with Hepatic fat fraction sub-groups as stratification factor by visit (FAS population)

Proportion of subjects with normal ALT with Hepatic fat fraction sub-groups as stratification factor by visit (ITT population)

Proportion of subjects with normal ALT with Hepatic fat fraction sub-groups as stratification factor by visit (PP population)

Proportion of subjects with normal ALT with HbA1c sub-groups as stratification factor by visit (FAS population)

Proportion of subjects with normal ALT with HbA1c sub-groups as stratification factor by visit (ITT population)

Proportion of subjects with normal ALT with HbA1c sub-groups as stratification factor by visit (PP population)

Proportion of subjects with normal ALT with Fibrosis sub-groups as stratification factor by visit (FAS population)

Proportion of subjects with normal ALT with Fibrosis sub-groups as stratification factor by visit (ITT population)

Proportion of subjects with normal ALT with Fibrosis sub-groups as stratification factor by visit (PP population)

Proportion of subjects with normal ALT with Ballooning sub-groups as stratification factor by visit (FAS population)

Proportion of subjects with normal ALT with Ballooning sub-groups as stratification factor by visit (ITT population)

Proportion of subjects with normal ALT with Ballooning sub-groups as stratification factor by visit (PP population)

Proportion of subjects with normal ALT with Inflammation sub-groups as stratification factor by visit (FAS population)

Proportion of subjects with normal ALT with Inflammation sub-groups as stratification factor by visit (ITT population)

Proportion of subjects with normal ALT with Inflammation sub-groups as stratification factor by visit (PP population)

Proportion of subjects with normal ALT with ALT sub-groups as stratification factor by visit (FAS population)

Proportion of subjects with normal ALT with ALT sub-groups as stratification factor by visit (ITT population)

Proportion of subjects with normal ALT with ALT sub-groups as stratification factor by visit (PP population)

Proportion of subjects with 30% reduction in ALT by visit (FAS population)

Proportion of subjects with 30% reduction in ALT by visit (ITT population)

Proportion of subjects with 30% reduction in ALT by visit (PP population)

Proportion of subjects with 30% reduction in ALT with Hepatic fat fraction sub-groups as stratification factor by visit (FAS population)

Proportion of subjects with 30% reduction in ALT with Hepatic fat fraction sub-groups as stratification factor by visit (ITT population)

Proportion of subjects with 30% reduction in ALT with Hepatic fat fraction sub-groups as stratification factor by visit (PP population)

Proportion of subjects with 30% reduction in ALT with HbA1c sub-groups as stratification factor by visit (FAS population)

Proportion of subjects with 30% reduction in ALT with HbA1c sub-groups as stratification factor by visit (ITT population)

Proportion of subjects with 30% reduction in ALT with HbA1c sub-groups as stratification factor by visit (PP population)

Proportion of subjects with 30% reduction in ALT with Fibrosis sub-groups as stratification factor by visit (FAS population)

Proportion of subjects with 30% reduction in ALT with Fibrosis sub-groups as stratification factor by visit (ITT population)

Proportion of subjects with 30% reduction in ALT with Fibrosis sub-groups as stratification factor by visit (PP population)

Proportion of subjects with 30% reduction in ALT with Ballooning sub-groups as stratification factor by visit (FAS population)

Proportion of subjects with 30% reduction in ALT with Ballooning sub-groups as stratification factor by visit (ITT population)

Proportion of subjects with 30% reduction in ALT with Ballooning sub-groups as stratification factor by visit (PP population)

Proportion of subjects with 30% reduction in ALT with Inflammation sub-groups as stratification factor by visit (FAS population)

Proportion of subjects with 30% reduction in ALT with Inflammation sub-groups as stratification factor by visit (ITT population)

Proportion of subjects with 30% reduction in ALT with Inflammation sub-groups as stratification factor by visit (PP population)

Proportion of subjects with 30% reduction in ALT with ALT sub-groups as stratification factor by visit (FAS population)

Proportion of subjects with 30% reduction in ALT with ALT sub-groups as stratification factor by visit (ITT population)

Proportion of subjects with 30% reduction in ALT with ALT sub-groups as stratification factor by visit (PP population)

Glucose metabolism markers (A1c, HOMA-IR, glucose, insulin) by visit (FAS population)

Glucose metabolism markers (A1c, HOMA-IR, glucose, insulin) by visit (ITT populations)

Glucose metabolism markers (A1c, HOMA-IR, glucose, insulin) by visit (PP population)

Glucose metabolism markers (A1c, HOMA-IR, glucose, insulin) by visit with hepatic fat fraction sub-groups as stratification factor (FAS population)

Glucose metabolism markers (A1c, HOMA-IR, glucose, insulin) by visit with hepatic

fat fraction sub-groups as stratification factor (ITT populations)

Glucose metabolism markers (A1c, HOMA-IR, glucose, insulin) by visit with hepatic fat fraction sub-groups as stratification factor (PP population)

Glucose metabolism markers (A1c, HOMA-IR, glucose, insulin) by visit with HbA1c sub-groups as stratification factor (FAS population)

Glucose metabolism markers (A1c, HOMA-IR, glucose, insulin) by visit with HbA1c sub-groups as stratification factor (ITT populations)

Glucose metabolism markers (A1c, HOMA-IR, glucose, insulin) by visit with HbA1c sub-groups as stratification factor (PP population)

Glucose metabolism markers (A1c, HOMA-IR, glucose, insulin) by visit with Fibrosis sub-groups as stratification factor (FAS population)

Glucose metabolism markers (A1c, HOMA-IR, glucose, insulin) by visit with Fibrosis sub-groups as stratification factor (ITT populations)

Glucose metabolism markers (A1c, HOMA-IR, glucose, insulin) by visit with Fibrosis sub-groups as stratification factor (PP population)

Glucose metabolism markers (A1c, HOMA-IR, glucose, insulin) by visit with Ballooning sub-groups as stratification factor (FAS population)

Glucose metabolism markers (A1c, HOMA-IR, glucose, insulin) by visit with Ballooning sub-groups as stratification factor (ITT populations)

Glucose metabolism markers (A1c, HOMA-IR, glucose, insulin) by visit with Ballooning sub-groups as stratification factor (PP population)

Glucose metabolism markers (A1c, HOMA-IR, glucose, insulin) by visit with Inflammation sub-groups as stratification factor (FAS population)

Glucose metabolism markers (A1c, HOMA-IR, glucose, insulin) by visit with Inflammation sub-groups as stratification factor (ITT populations)

Glucose metabolism markers (A1c, HOMA-IR, glucose, insulin) by visit with Inflammation sub-groups as stratification factor (PP population)

Glucose metabolism markers (A1c, HOMA-IR, glucose, insulin) by visit with ALT sub-groups as stratification factor (FAS population)

Glucose metabolism markers (A1c, HOMA-IR, glucose, insulin) by visit with ALT sub-groups as stratification factor (ITT populations)

Glucose metabolism markers (A1c, HOMA-IR, glucose, insulin) by visit with ALT sub-groups as stratification factor (PP population)

Body mass index, waist circumference and waist:hip ratio by visit (FAS population)

Body mass index, waist circumference and waist:hip ratio by visit (ITT population)

Body mass index, waist circumference and waist:hip ratio by visit (PP population)

Body mass index, waist circumference and waist:hip ratio by visit with hepatic fat fraction sub-groups as stratification factor (FAS population)

Body mass index, waist circumference and waist:hip ratio by visit with hepatic fat fraction sub-groups as stratification factor (ITT population)

Body mass index, waist circumference and waist:hip ratio by visit with hepatic fat fraction sub-groups as stratification factor (PP population)

Body mass index, waist circumference and waist:hip ratio by visit with HbA1c sub-groups as stratification factor (FAS population)

Body mass index, waist circumference and waist:hip ratio by visit with HbA1c sub-

groups as stratification factor (ITT population)

Body mass index, waist circumference and waist:hip ratio by visit with HbA1c sub-groups as stratification factor (PP population)

Body mass index, waist circumference and waist:hip ratio by visit with Fibrosis sub-groups as stratification factor (FAS population)

Body mass index, waist circumference and waist:hip ratio by visit with Fibrosis sub-groups as stratification factor (ITT population)

Body mass index, waist circumference and waist:hip ratio by visit with Fibrosis sub-groups as stratification factor (PP population)

Body mass index, waist circumference and waist:hip ratio by visit with Ballooning sub-groups as stratification factor (FAS population)

Body mass index, waist circumference and waist:hip ratio by visit with Ballooning sub-groups as stratification factor (ITT population)

Body mass index, waist circumference and waist:hip ratio by visit with Ballooning sub-groups as stratification factor (PP population)

Body mass index, waist circumference and waist:hip ratio by visit with Inflammation sub-groups as stratification factor (FAS population)

Body mass index, waist circumference and waist:hip ratio by visit with Inflammation sub-groups as stratification factor (ITT population)

Body mass index, waist circumference and waist:hip ratio by visit with Inflammation sub-groups as stratification factor (PP population)

Body mass index, waist circumference and waist:hip ratio by visit with ALT sub-groups as stratification factor (FAS population)

Body mass index, waist circumference and waist:hip ratio by visit with ALT sub-groups as stratification factor (ITT population)

Body mass index, waist circumference and waist:hip ratio by visit with ALT sub-groups as stratification factor (PP population)

Serum lipid profile by visit (FAS population)

Serum lipid profile by visit (ITT population)

Serum lipid profile by visit (PP population)

Serum lipid profile by visit with hepatic fat fraction sub-groups as stratification factor (FAS population)

Serum lipid profile by visit with hepatic fat fraction sub-groups as stratification factor (ITT population)

Serum lipid profile by visit with hepatic fat fraction sub-groups as stratification factor (PP population)

Serum lipid profile by visit with HbA1c sub-groups as stratification factor (FAS population)

Serum lipid profile by visit with HbA1c sub-groups as stratification factor (ITT population)

Serum lipid profile by visit with HbA1c sub-groups as stratification factor (PP population)

Serum lipid profile by visit with Fibrosis sub-groups as stratification factor (FAS population)

Serum lipid profile by visit with Fibrosis sub-groups as stratification factor (ITT population)

population)

Serum lipid profile by visit with Fibrosis sub-groups as stratification factor (PP population)

Serum lipid profile by visit with Fibrosis sub-groups as stratification factor (FAS population)

Serum lipid profile by visit with Fibrosis sub-groups as stratification factor (ITT population)

Serum lipid profile by visit with Fibrosis sub-groups as stratification factor (PP population)

Serum lipid profile by visit with Inflammation sub-groups as stratification factor (FAS population)

Serum lipid profile by visit with Inflammation sub-groups as stratification factor (ITT population)

Serum lipid profile by visit with Inflammation sub-groups as stratification factor (PP population)

Serum lipid profile by visit with ALT sub-groups as stratification factor (FAS population)

Serum lipid profile by visit with ALT sub-groups as stratification factor (ITT population)

Serum lipid profile by visit with ALT sub-groups as stratification factor (PP population)

Liver function profile (ALT, AST, GGT, Bilirubin, albumin) by visit (FAS population)

Liver function profile (ALT, AST, GGT, Bilirubin, albumin) by visit (ITT population)

Liver function profile (ALT, AST, GGT, Bilirubin, albumin) by visit (PP population)

Liver function profile (ALT, AST, GGT, Bilirubin, albumin) by visit with hepatic fat fraction sub-groups as stratification factor (FAS population)

Liver function profile (ALT, AST, GGT, Bilirubin, albumin) by visit with hepatic fat fraction sub-groups as stratification factor (ITT population)

Liver function profile (ALT, AST, GGT, Bilirubin, albumin) by visit with hepatic fat fraction sub-groups as stratification factor (PP population)

Liver function profile (ALT, AST, GGT, Bilirubin, albumin) by visit with HbA1c sub-groups as stratification factor (FAS population)

Liver function profile (ALT, AST, GGT, Bilirubin, albumin) by visit with HbA1c sub-groups as stratification factor (ITT population)

Liver function profile (ALT, AST, GGT, Bilirubin, albumin) by visit with HbA1c sub-groups as stratification factor (PP population)

